8.11.4.3 Survival Follow-up Contacts

Participant survival follow-up status will be assessed approximately every 12 weeks to assess for vital status until death, withdrawal of consent, or the end of the study, whichever occurs first.

The first Survival Follow-up assessment should be scheduled as described below:

- 1. For participants who discontinue treatment intervention and who will not enter Efficacy Follow-up, the first Survival Follow-up contact will be scheduled 12 weeks after the Discontinuation Visit and/or Safety Follow-up Visit (whichever is last).
- 2. For participants who completed assessments in Efficacy Follow-up, the first Survival Follow-up contact will be scheduled 12 weeks after the last efficacy assessment follow-up visit has been performed.

Protocol Amendment 04 implementation: Survival follow-up contacts are not required. Participants currently on study treatment will have the safety follow-up visit as the final visit. Participants currently in survival follow-up are considered to have completed the study.

8.11.5 Vital Status

Protocol Amendment 04 implementation : There will be no collection of vital status for participants. Participants currently on study treatment will have the safety follow-up visit as the final visit.

To ensure current and complete survival information (vital status) is available at the time of database locks, updated vital status may be requested during the study by the Sponsor. For example, updated vital status may be requested before but not limited to, an eDMC review, interim and/or final analysis. Upon Sponsor notification, all participants who do not/will not have a scheduled study visit or study contact during the Sponsor-defined period will be contacted for their vital status.

9 STATISTICAL ANALYSIS PLAN

At implementation of Amendment 05, the below changes apply. The changes listed below supersede any protocol content/instructions from previous amendments.

- Participants with access to approved SOC (eg, immunotherapy, chemotherapy, targeted therapy) should be considered for discontinuation from the study. Those benefiting from atezolizumab, but unable to access it as SOC outside the study, may continue on study and receive treatment with atezolizumab until discontinuation criteria are met. The final required study visit will be the Safety Follow-up Visit.
- Participants who complete study treatment or otherwise meet EOT criteria will be discontinued from the study after the EOT visit and any required safety follow-up visit.
- There will be no follow up for survival status. Participants currently in imaging follow-up or survival follow-up are considered to have completed the study and therefore should obtain imaging and further oncological care as per local SOC. Standard safety reporting should, however, continue, as applicable.
- Participants remaining on study at the time of Amendment 05 should continue to be monitored in the study through the AE reporting period (Section 8.4).

Existing protocol content is retained for historical reference.

Protocol Amendment 04 implementation: based on recommendations of the eDMC following the interim efficacy/safety analysis (data cutoff 04-JUN-2024) which showed that the primary endpoint of overall survival met the pre-specified futility criteria, the study was unblinded, the experimental arm (Arm A: MK-7684A) will be discontinued and all ongoing participants on MK-7684A treatment will be offered the option to move to the comparator arm (Arm B: atezolizumab monotherapy) for the remainder of the study. The prespecified final analysis of the study described in the SAP will not be performed. Safety analysis will be performed at the end of the study. There will be no further analyses for efficacy and ePRO endpoints collected from participants after IA cutoff date.

This section outlines the statistical analysis strategy and procedures for the study. If, after the study has begun, but prior to any unblinding/final database lock, changes are made to primary and/or key secondary hypotheses, or the statistical methods related to those hypotheses, then the protocol will be amended (consistent with ICH Guideline E9). Changes to exploratory or other nonconfirmatory analyses made after the protocol has been finalized, but prior to the conduct of any analysis, will be documented in a sSAP and referenced in the CSR for the study. Post hoc exploratory analyses will be clearly identified in the CSR. Other planned analyses (ie, those specific to the analysis of ePROs) will be documented in an sSAP.

9.1 Statistical Analysis Plan Summary

Key elements of the SAP are summarized below; the comprehensive plan is provided in Section 9.2 through Section 9.12.

Protocol Amendment 04 implementation: the prespecified final analysis of the study described in the SAP will not be performed. Information regarding planned final analysis in Section 9 is being retained for historical purposes. Safety analysis will be performed at the end of the study. There will be no further analyses of efficacy and ePRO endpoints collected from participants after IA cutoff date.

Study Design Overview	This is a Phase 3, randomized, double-blind, active-controlled, multisite study of MK-7684A combined with etoposide/platinum chemotherapy followed by MK-7684A compared to atezolizumab combined with etoposide/platinum chemotherapy followed by atezolizumab in the first-line treatment of ES-SCLC.		
Treatment Assignment	Approximately 450 participants will be randomized in a 1:1 ratio between 2 treatment groups: (1) the MK-7684A in combination with etoposide/platinum arm and (2) the atezolizumab in combination with etoposide/platinum arm. Stratification factors are:		
	• ECOG performance status at Baseline (0 vs. 1)		
	• LDH at Baseline (\leq ULN vs > ULN)		
	• Liver metastases at Screening: Yes or No		
	• Brain metastases at Screening: Yes or No		
	This is a randomized double-blind study.		
Analysis Populations	Efficacy: Intention-to-Treat (ITT)		
	Safety: All Participants as Treated (APaT)		
	PRO: Full Analysis Set (FAS)		
Primary	Overall survival (OS)		
Endpoints/Hypotheses			
Secondary Endpoints/Hypotheses	• PFS per RECIST 1.1 by BICR		
	• ORR per RECIST 1.1 assessed by BICR		
	• DOR per RECIST 1.1 assessed by BICR		
	• Safety and tolerability		
	• ePROs		

Statistical Methods for Key Efficacy Analyses	The primary and secondary hypothesis will be evaluated by comparing MK-7684A in combination with etoposide/platinum to atezolizumab in combination with etoposide/platinum on OS and PFS using stratified log-rank tests. Estimation of the hazard ratio (HR) will be performed using a stratified Cox regression model. Event rates over time will be estimated within each treatment group using the Kaplan-Meier method.
Statistical Methods for Key Safety Analyses	The analysis of safety results will follow a tiered approach. The tiers differ with respect to the analyses that will be performed. There are no Tier 1 events in this study. Tier 2 parameters will be assessed via point estimates with 95% confidence intervals provided for between-group comparisons; only point estimates by treatment group are provided for Tier 3 safety parameters. The 95% confidence intervals for the between-treatment differences in percentages will be provided using the Miettinen and Nurminen method.
Multiplicity	

Sample Size and Power	The planned sample size is approximately 450 participants.

9.2 Responsibility for Analyses/In-house Blinding

The statistical analysis of the data obtained from this study will be the responsibility of the Clinical Biostatistics department of the Sponsor.

This study will be conducted as a double-blind study under in-house blinding procedures. The official, final database will not be unblinded until medical/scientific review has been performed, protocol deviations have been identified, and data have been declared final and complete.

The Clinical Biostatistics department will generate the randomized allocation schedule(s) for study intervention assignment for this protocol, and the randomization will be implemented in an interactive voice response system.

Protocol Amendment 04 implementation: following eDMC review of data at IA, the study was unblinded.

9.3 Hypotheses/Estimation

Objectives and hypotheses of the study are stated in Section 3.

9.4 Analysis Endpoints

9.4.1 Efficacy Endpoints

Primary

• Overall Survival (OS)

OS is defined as the time from randomization to death due to any cause.

Secondary

08RNJZ

• Progression-free survival (PFS)

PFS is defined as the time from randomization to the first documented disease progression per RECIST 1.1 by BICR or death due to any cause, whichever occurs first.

• Objective Response Rate (ORR)

The ORR is defined as the percentage of participants who achieve a confirmed complete response (CR) or partial response (PR) per RECIST 1.1 as assessed by BICR.

• Duration of Response (DOR)

For participants with confirmed CR or PR, DOR is defined as the time from the first documented evidence of CR or PR until disease progression or death due to any cause, whichever occurs first.

9.4.2 Safety Endpoints

Safety and tolerability will be assessed by clinical review of all relevant parameters, including AEs, laboratory values, and vital signs.

9.4.3 Patient-reported Outcome Endpoints

The following secondary PRO endpoints will be evaluated as described in Section 4.2.2.3 and analyzed as described in Section 9.6.3:

- Change from baseline in Global Health Status/QoL scale (EORTC QLQ-C30 Items 29 and 30)
- Physical functioning scale (EORTC QLQ-C30 Items 1 through 5)
- Single-item symptom scales: cough (EORTC QLQ-LC13 Item 31), chest pain (EORTC QLQ-LC13 Item 40), and dyspnea (EORTC QLQ-C30 Item 8)

Time-to-true deterioration (TTD) in

- Global Health Status/QoL scale (QLQ-C30 items 29-30)
- Single-item symptom scales: cough (QLQ-LC13 item 31), chest pain (QLQ-LC13 item 40), and dyspnea (QLQ-C30 item 8)
- Physical functioning scale (QLQ-C30 items 1-5)

Based on prior literature [Osoba, D., et al 1998] [King, M. T. 1996], a 10-point or greater worsening from baseline for each scale represents a clinically relevant deterioration. TTD is defined as the time to first onset of 10 or more (out of 100) deterioration from baseline in a given scale/subscale/item and confirmed by a second adjacent 10 or more deterioration from baseline.

9.5 Analysis Populations

9.5.1 Efficacy Analysis Populations

The analyses of efficacy endpoints are based on the intention-to-treat (ITT) population. All randomized participants will be included in this population. Participants will be analyzed in the treatment group to which they are randomized.

9.5.2 Safety Analysis Populations

Safety Analyses will be conducted in the All Participants as Treated (APaT) population, which consists of all randomized participants who received at least 1 dose of study intervention. Participants will be included in the treatment group corresponding to the study intervention they actually received for the analysis of safety data using the APaT population. This will be the treatment group to which they are randomized except for participants who take incorrect study intervention for the entire treatment period; such participants will be included in the treatment group corresponding to the study intervention actually received. Any participant who receives the incorrect study intervention for 1 cycle, but receives the correct treatment for all other cycles, will be analyzed according to the correct treatment group and a narrative will be provided for any events that occur during the cycle for which the participant is incorrectly dosed.

At least 1 laboratory or vital sign measurement obtained after at least 1 dose of study intervention is required for inclusion in the analysis of each specific parameter. To assess change from baseline, a baseline measurement is also required.

9.5.3 **PRO Analysis Populations**

The PRO analyses are based on the PRO Full Analysis Set (PRO FAS) Population, defined as all randomized participants who have at least one PRO assessment available for the specific endpoint and have received at least one dose of the study intervention. Participants will be analyzed in the treatment group to which they are randomized.

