4.1 Overall Design

Protocol Amendment 04 implementation: Based on recommendations of the eDMC following an interim review showed that the primary endpoint of OS met the prespecified futility criteria, study was unblinded, and the experimental arm (Arm A: MK-7684A) was discontinued. All ongoing participants on treatment were offered an option to move to the comparator arm (Arm B: atezolizumab monotherapy) for the remainder of the study.

This is a Phase 3, randomized, double-blind, active-controlled, multisite study of MK-7684A combined with etoposide/platinum chemotherapy followed by MK-7684A compared to atezolizumab combined with etoposide/platinum chemotherapy followed by atezolizumab in the first-line treatment of ES-SCLC.

Following a screening period of up to 28 days, approximately 450 eligible participants will be randomized 1:1 into 2 intervention groups:

Group A – Participants will receive 4 cycles of etoposide/platinum chemotherapy in combination with MK-7684A followed by MK-7684A until any of the conditions for discontinuation are met (Section 7.1).

Group B – Participants will receive 4 cycles of etoposide/platinum chemotherapy in combination with atezolizumab followed by atezolizumab until any of the conditions for discontinuation are met (Section 7.1).

Crossover will not be allowed between the intervention groups. A double-blinding technique will be used for atezolizumab and MK-7684A assignment. The chemotherapy agents will be open-label. The choice of platinum (cisplatin or carboplatin) in both arms is selected by the investigators before randomization.

Treatment randomization will be stratified according to ECOG performance status (0 or 1), LDH (\leq ULN or >ULN), presence of liver metastases (yes or no), and presence of brain metastases (yes or no).

Specific procedures to be performed during the study, including prescribed times and associated visit windows, are outlined in Section 1.3 of the SoA. Details of each procedure are provided in Section 8.

Tumor response will be evaluated per RECIST 1.1 and participants will have posttreatment follow-up imaging for disease status until any of the conditions for discontinuation of imaging are met (Section 8.2.1.3). All participants will be followed for overall survival until death, withdrawal of consent, or the end of the study.

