8.3 Safety Assessments

Details regarding specific safety procedures/assessments to be performed in this study are provided. The total amount of blood/tissue to be drawn/collected over the course of the study (from prestudy to poststudy visits), including approximate blood/tissue volumes drawn/collected by visit and by sample type per participant, can be found in the Laboratory Manual.

Planned time points for all safety assessments are provided in the SoA.

Protocol Amendment 04 implementation: Safety assessments and safety related data collection including laboratory assessments should be followed per SoA for participants who continue study therapy.

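### Section 9.5.2 leaves Arm A participants who moved to atezolizumab in the MK-7684A safety group, so their post-switch safety data and cycles can be tabulated under MK-7684A

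*Combined protocol and SAP*

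**What the plan says.** Section 9.5.2 defines the All Participants as Treated population. Its general principle is: "Participants will be included in the treatment group corresponding to the study intervention they actually received". The next sentence says what that means in practice: "This will be the treatment group to which they are randomized except for participants who take incorrect study intervention for the entire treatment period". Those exceptional participants are counted under the drug they took. A last rule covers one misdosed cycle: the participant stays in the correct group and a narrative is written.

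These rules suit the design in Section 4.1 before Amendment 04: "Crossover will not be allowed between the intervention groups". Amendment 04 changed that. According to the Synopsis and Section 9, Arm A participants still on treatment stopped MK-7684A and were offered atezolizumab monotherapy. For the remaining analyses Section 9 says: "Safety analysis will be performed at the end of the study". It ends efficacy and ePRO analyses of data collected after the interim cutoff, but sets no such limit for safety.

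Safety data collection goes on. Section 8.3 says: "Safety assessments and safety related data collection including laboratory assessments should be followed per SoA for participants who continue study therapy". Under Amendment 05, participants who benefit from atezolizumab and cannot obtain it elsewhere "may continue on study and receive treatment with atezolizumab until discontinuation criteria are met".

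Section 9.12 defines exposure as the number of cycles in which study medication was infused, summarized for the same population. It names no drug. Its cross-reference goes to Section 8.6 (Pharmacokinetics), which does not define the term.

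**The concern.** A grouping rule written for a trial without crossover now governs a trial in which one arm was offered the other arm's drug. Each participant carries one label for all their data. For someone who took MK-7684A and then atezolizumab, no single label describes both periods.

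What is at stake is attribution in the end-of-study safety tables. Events that begin on atezolizumab would be listed as events of the MK-7684A arm. Post-switch laboratory values could enter that arm's toxicity shifts, and its exposure summary could include cycles of another drug. A reader of those tables could not tell the two periods apart.

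**Working it through.** The plan states no figure for this point, so there is none to reproduce. The check is mainly one of text, followed by a scale.

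**1. Does a participant who moved meet an exception in 9.5.2?** The main exception needs the wrong drug throughout treatment. This participant had already received MK-7684A as randomized, and the atezolizumab was offered by the protocol: Table 4 lists it for all participants. The one-cycle rule concerns a single dosing error. Neither applies, so the group remains MK-7684A.

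**2. Are data still generated after the switch?** Yes. Section 8.3 keeps safety assessments for those who continue therapy. Section 8.4.1 requires adverse events to be reported until 30 days after study intervention ends, and serious ones until 90 days (30 if new anticancer therapy starts). Section 6 defines study intervention broadly enough to include atezolizumab, so reporting does not end with the last MK-7684A dose.

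**3. Does other readable text divide the data?** The Amendment 04 text in Sections 9, 9.1 and 9.7 applies the interim cutoff only to efficacy and ePRO data. Sections 9.5.2 and 9.6.2, Table 14 and the Amendment 05 bullets contain no cut, censoring rule or separate column for post-switch data.

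**4. Exposure.** Section 9.12 counts infusion cycles per participant without naming a drug. If exposure is shown by the 9.5.2 groups, atezolizumab cycles after the switch can be added to the MK-7684A arm.

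**5. Scale.** Inputs: about 450 participants, 1:1 (Section 9.9); Tier 2 cut-off for serious events of 1% in one group (Section 9.6.2). Assumption: nearly all randomized participants were dosed.

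- Arm A: 450 / 2 = 225.
- One participant with a first occurrence of an event type after the switch: 1 / 225 = 0.44 percentage points.
- Three or six such participants (assumed counts): 3 / 225 = 1.33 points; 6 / 225 = 2.67 points.
- Serious-event cut-off: 0.01 × 225 = 2.25, so 3 participants. Three first post-switch cases of one serious term would by themselves bring that term into Tier 2.

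A participant who already had the event type before the switch, for example during chemotherapy, adds nothing to its incidence.

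**6. What lies outside the problem.** The "interim efficacy/safety analysis (data cutoff 04-JUN-2024") comes 65 days before the investigator letter of 08-AUG-2024 that communicated the changes: 26 days left in June + 31 in July + 8 in August = 65. Its safety results contain no data from this switch.

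**The case against.** The strongest reply has four parts.

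- **A rule may exist elsewhere.** Section 9 sends this kind of change to a supplemental SAP: "Changes to exploratory or other nonconfirmatory analyses made after the protocol has been finalized, but prior to the conduct of any analysis". That document is not available here, and parts of Section 9 are redacted. This stands as a limit: the check shows that the readable plan has no split, not that none exists.
- **The SAP text is partly historical.** Section 9 says existing content is kept for reference, so applying 9.5.2 to the end-of-study safety analysis is an inference. It is a reasonable one: that analysis is still promised, and 9.5.2 is the only readable rule for grouping it.
- **Keeping randomized groups is a recognizable choice.** It is definite, and it adds events to the MK-7684A column rather than hiding them. But it still reports events on one drug under another without marking them.
- **Little depends on it.** The interim analysis gives a comparison free of switch data, MK-7684A has been stopped, and Section 9.6.2 calls the Tier 2 intervals descriptive. Amendment 05 also asks that participants with access to approved standard of care be considered for leaving the study, which would shorten post-switch exposure. All of this stands and keeps the point minor.

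A reader might infer that the wording about moving to the comparator arm makes 9.5.2 ambiguous, or transfers these participants' whole record to atezolizumab. The sentence defining the group by randomization settles that. A reader might also infer that the safety analysis is the only analysis left. Section 9 rules out only the planned final analysis and further efficacy and ePRO analyses of post-cutoff data; it does not cancel every other analysis.

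**Conclusion.** The point holds as a minor one. Followed as written, 9.5.2 places post-switch events, laboratory values and vital signs under MK-7684A in the end-of-study safety analysis, and 9.12 allows atezolizumab cycles to be counted as that arm's exposure.

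The total effect cannot be computed, because neither the number who moved nor their event rates are given. The only firm figure is about 0.44 points per participant with a first-ever occurrence after the switch, which assumes about 225 treated in Arm A. Participants who did not move, and data before the first atezolizumab dose, are unaffected.

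Two stronger conclusions are not supported. The futility finding and the interim safety results are not distorted, because their cutoff precedes the switch. Nor does every post-switch event belong to atezolizumab: Section 6.6.1 says immune-related events can appear several months after the last dose, so some may be due to earlier MK-7684A. The conclusion also assumes that the supplemental SAP has no rule on this.

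**What to change.** Add a rule to 9.5.2, 9.6.2 and 9.12 for participants who moved from Arm A to atezolizumab. It can instead go in the supplemental SAP before the end-of-study safety analysis is run; if a rule is already there, cross-refer to it from 9.5.2.

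1. MK-7684A summaries of events, laboratory values and vital signs include data up to the first atezolizumab dose.
2. Data from that dose onward appear in a separate column, *after switch to atezolizumab*, with a footnote that delayed immune-related events may be due to earlier MK-7684A.
3. If the sponsor prefers a carry-over period after the last MK-7684A dose, define it explicitly as a new analysis window and flag events that overlap with atezolizumab. The 8.4.1 windows cannot simply be cited, because they run from the end of study intervention, not from the last MK-7684A dose.
4. Summarize exposure cycles by drug, and correct the cross-reference to Section 8.6.

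The cost is a few sentences and one extra output column, plus a flag if a carry-over window is used. Dose dates are already recorded in the CRF (Section 6.4), so no new data are needed. The drawback is that some delayed MK-7684A events will fall in the post-switch column, which is why the footnote is needed.
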